9. STUDY ASSESSMENTS

9.1 Study flow and assessments

The frequency of assessments and FUP visits are detailed in the Study schedule section with a patient timeline on page 27 and Study flow on page 29.

Before discharge, the parent (and patient) will be thoroughly instructed by the local investigators about the further study schedule. If applicable, the information will contain details about the correct storage and administration of the IMP, the precise measurement of VS and its documentation in secuTrial® or study diary, as well as the procedure in case of progression and/or deterioration of disease.

9.2 Assessments of outcomes

9.2.1 Assessment of co-primary outcomes

1.1: Time to normalization of all VS (efficacy)

The index time point for the assessment will be defined as the last VS measurement in the ED prior to IMP administration (or prior to the administration of antipyretic medication at the ED). VS will be measured after having the patient relax (without running, crying, etc. for at least 5min). Measurements will be taken until VS (T, RR, HR, and SpO₂) are normalized in 3 consecutive measurements within 24 hours (section 5.1).

The VS measurement method will depend on the patient care status:

Hospitalized patients:

VS will be measured by routine clinical monitoring every 8h after the index time point using locally available equipment and procedures: T by ear thermometer; HR and SpO₂ by pulse oximeter on room air; RR by clinical assessment. VS will be documented in the clinical information system and in secuTrial®.

Ambulatory patients:

VS will be measured 3x/24h (the first time within 8h after the index time point) until 3 consecutive normal measurements of all VS within 24h are documented. The parent will receive a [trial box](#) including the following items:

- IMP (labelled)
- Ear thermometer
- Masimo SafetyNet™ Radius PPG™
- Study diary and instructions for the use of the patient self-documentation with secuTrial®
- Instruction sheet (incl. QR code to the MYTHIC website)

The ear thermometer for temperature measurement will be standardized and is a validated medical device with memory function to verify the data entry in the patient self-documentation with secuTrial®.

The Masimo SafetyNet™ Radius PPG™ will be used to measure SpO₂, respiratory rate, and heart rate. Masimo SafetyNet™ is a commercial available CE mark sensor that can be connected to a secure, cloud-based patient management platform allowing for spot-checking and continuous measurements. Patients will receive a multi-day supply of disposable Radius PPG™ sensors, along with access to the Masimo SafetyNet™ mobile application (Masimo SafetyNet™ App).

Patients will have access to their personal data and health information on their mobile device through the Masimo SafetyNet™ App. When the patient uninstalls the Masimo SafetyNet™ App or “deletes” his or her account, all personal data held by Masimo or stored on the Masimo SafetyNet™ App is permanently deleted. All personal data is encrypted at rest and in transit across public networks. Masimo is HDS:2018 certified. Masimo operates an Information Security Management System for Health Information Hosting Provision that complies to the requirements of HDS Certification Standard – Requirements and Controls – rev. 1.1 of June 2018. Masimo SafetyNet™'s data is processed and stored on a private “cloud” server provided by Amazon Web Services (AWS). The server resides in Germany with a backup server in Ireland. AWS' cloud services are certified for compliance with multiple widely

recognized and accepted data security standards. Only authorized registered staff of the TMT has access to Masimo SafetyNet™ Clinician Portal with individual authentication. Masimo and AWS have taken comprehensive steps to comply with the EU General Data Protection Regulation (“GDPR”). In case that participants do not have a personal device where the Masimo SafetyNet™ App can be installed study-specific mobile devices will be handed out in exchange of a deposit.

Each Patient will register to the Masimo SafetyNet™ App with a personal and de-identified email address, which will be specifically generated for the MYTHIC study. No identifying information will be entered into the Masimo SafetyNet™ App. Patients will be asked to perform spot-checks and to transfer displayed parameters on their mobile device into their study diary or directly into the patient self-documentation with secuTrial®.

Measurements will be documented via patient self-documentation with secuTrial® or study diary. The patients will be able to choose between these two self-documentation methods. If parents choose to use the patient self-documentation with secuTrial®, the study team will generate a user profile for the patient within secuTrial®. Next, the person holding the user profile will receive two different emails: the first email contains the User-ID and the link to the data capture site for data entry on mobile devices. The second email contains a link for the user to set a password. After the user defines a personal password, the data capture site can be reached. The user will only have access to their own data and eCRFs, which have been previously assigned to the patient. One prerequisite for the use of the patient self-documentation with secuTrial® is access to the internet, as data capture cannot be inserted offline. If parents choose to use the study diary, they will be provided with a paper-based and pre-printed study diary for data capture. This data will then be entered manually by the study team into the secuTrial® system. The patient self-documentation with secuTrial® or study diary will inform the parent about age-specific normal ranges of VS. The trial box will be returned at the close-out visit including the IMP bottles to measure the remnant of suspension in bottles. Upon return at the local study center, trial boxes will be cleaned, devices connected (for data export), controlled, recharged, and thoroughly disinfected at the local study site. Return status of trial boxes and data on paper included in the study diary will be recorded in the eCRF. Trial boxes will be distributed to each participating center so that at least 5(-10) trial boxes are in stock on site at any given time.

1.2: CAP-related change in patient care status (safety)

Any change in patient care status from ambulatory to hospitalized (admission or re-admission) or from hospitalized on general ward to ICU (transfer) within 28 days after randomization will be documented by local investigators during each FUP visit (section 5.1). (Re-)Admission will be assumed to be CAP-related if the same constellation of clinical signs as outlined in the inclusion criteria (“Clinical diagnosis of CAP”) is present (section 7.1). At each FUP visit, the parent (and patient) will be asked to report (re-)admissions and whether these were due to on-going or relapsing signs and symptoms of CAP, because of another infection, or for another reason. In case of (re-)admission at nonparticipating centers, the parent (and child) will be asked for permission to request medical reports.

9.2.2 Assessment of secondary outcomes

2.1: Overall clinical outcome based on benefits and harms (DOOR)

“Adequate clinical response” (section 5.2, Table 3) and “solicited AEs” (section 5.2, Table 3) will be documented and ranked according to DOOR (section 5.2) [65] on day 3 (in-hospital visit), day 5 (end of treatment), day 7, 14, 21 (phone calls), and day 28 (close-out visit) by local investigators or delegated staff. Ambulatory patients will be asked to enter the day-5 assessment in the patient self-documentation with secuTrial® or study diary.

2.2: Time (days) to normalization of CAP-related symptoms

CAP-related symptoms according to a validated measure for childhood respiratory infections [68, 69] (i.e., cough, shortness of breath, wheeze, chest pain, congestion and/or rhinorrhea, sore throat, ear pain, pallor, headache, muscle aches or muscle pains, reduced food or fluid intake, not sleeping well, interference with normal activity) will be documented 1x/24h until normalization depending on the patient care status either in the clinic information system or in the patient self-documentation with secuTrial® or study diary by the parent (and patient).

2.3: QoL assessment of patients and their families

A standardized and validated QoL questionnaire (Appendices, section 17.4) [70] will be answered by the parent (and patient) in the patient self-documentation with secuTrial® or study diary on day 3 (in-hospital visit) and day 28 (close-out visit). At the FUP visits on days 7, 14, and 21, the questionnaire will be answered during the phone calls.

2.4: Time (days) to return to daily routine, defined as return to childcare/school/work of patients and their families

Exact dates of return to childcare or school (patient) and return to work (parent) will be documented in the patient self-documentation with secuTrial® or study diary and reported by parent at the FUP visits until day 28 after randomization.

2.5: Development of Mp-associated extrapulmonary manifestations

The following signs/symptoms/syndromes suggestive of Mp-associated extrapulmonary manifestations as described in [71] will be assessed by evaluation of the patient during hospitalization or in-hospital visits (day 3 and 28):

- Dermatological (e.g., maculopapular skin eruptions, mucositis, urticaria, erythema multiforme, Stevens-Johnson syndrome)
- Eye involvement (e.g., conjunctivitis, uveitis)
- Neurological (e.g., aseptic meningitis, encephalitis, myelitis, Guillain-Barré syndrome)
- Hematological (e.g., hemolytic anemia)
- Cardiovascular (e.g., pericarditis, Kawasaki-like disease)
- Digestive organ involvement (e.g., hepatitis, pancreatitis)
- Musculoskeletal (e.g., arthritis, rhabdomyolysis)
- Urogenital (e.g., glomerulonephritis)

9.2.3 Assessment of additional outcomes

Other outcomes of interest (section 5.3) will be assessed by direct observation and evaluation of the patient, collection of data from routine electronic healthcare records at participating centers, and parental reports during in-hospital visits or FUP phone calls.

Other additional outcomes independent of study intervention:

- Participants and their parents will be asked about their perception of the study film with different questions on a 5-point Likert scale at the close-out visit on day 28.

9.2.4 Assessment of safety outcomes

The assessment of safety outcomes is described in section 5.4. Safety outcomes will also be assessed by direct observation and evaluation of the patient, collection of data from routine electronic healthcare records at participating centers, and parental reports during in-hospital visits or FUP phone calls.

Safety outcomes include the following outcomes (the numbering for the objectives/outcomes is the same in each chapter and throughout the whole document, section 5.4):

Co-primary outcome:

1.2: Proportion of children with CAP-related change in patient care status

Secondary outcomes:

2.1: Overall clinical outcome based on benefits and harms (DOOR)

2.5: Development of Mp-associated extrapulmonary manifestations

Additional outcomes:

- Unscheduled medical visits
- (Re-)treatment with antibiotics
- Side effects/AEs/SAEs of IMP

9.2.4.1 Adverse events (AEs)

Solicited AEs will be asked from parental report and/or will be identified in routine electronic healthcare records at participating centers. Solicited AEs are summarized in section 5.2, Table 2. These solicited AEs will be used to determine **DOOR** (section 5.2).

9.2.4.2 Laboratory parameters

No clinical safety laboratory studies will be performed as part of this protocol.

Routine clinical care will provide the following laboratory parameters:

- Hematology assessment: hemoglobin (g/L), leukocytes (G/L), neutrophils (G/L), and erythrocyte sedimentation rate (mm/h).
- Biochemistry assessment: CRP (mg/L), PCT (ng/mL), sodium (mmol/L), and potassium (mmol/l).
- Microbiological investigations: respiratory sample (location [nasopharyngeal, oropharyngeal, other], type [swab, aspirate, other], method [multiplex-PCR, PCR, culture, antigen test, other], pathogen[s] detected, detection of antimicrobial resistances), and blood cultures (pathogen[s] detected, detection of antimicrobial resistances).

The following laboratory parameters will be assessed as part of the study (Study schedule, page 27):

- NPS for pathogen detection by multiplex PCR (Biofire® Filmarray® Respiratory 2.1 plus panel [Waites, 2017]), *Mp* genotyping and antimicrobial resistance determination [80] on days 1, 3, and 28. If a NPS is performed for clinical reasons, remaining sample will be stored locally (and transferred later in batches to the MYTHIC Biobank at University Children's Hospital Zurich) so that no more than one swab will be performed on patients on day 1. The study results will not be available before the close-out visit.
- Capillary blood on day 1 for *Mp* IgM LFA (as screening) and biomarkers, as well as on day 3 and 28 for biomarkers. The *Mp* IgM LFA results will be available within 10min and will be communicated to the treating physician as part of the inclusion criteria for the intervention phase. All other results will not be available before the close-out visit.
- If venous blood is available on day 1, *Mp* IgM LFA and biomarkers will be directly assessed from venous blood instead of capillary blood together with *Mp* IgM ASC ELISpot assay [22] and *Mp* IgM ELISA (Serion® ELISA classic Mycoplasma pneumoniae IgM/IgG/IgA [81]).

9.2.4.3 Vital signs

Vital signs will be recorded for the assessment of the co-primary objectives as described in section 9.2.1.

9.2.5 Assessments in participants who prematurely stop the study

As described in section 8.5, if consent is provided for contacting primary care providers and/or reviewing the routine electronic healthcare records at the recruiting center, the data of interest will primarily be focused on the co-primary outcomes.

9.3 Procedures at each visit

Study visits and contact schedules will be prepared for each patient at randomization, and patients will be followed on that schedule until the close-out visit even if IMP is discontinued prematurely. The target dates for study visits and contacts are determined by the calendar date of randomization and are not affected by subsequent events. The schedule defines study visit times (with windows) necessary for data collection (Study schedule, page 27). Study visits/contacts are scheduled as follows and will include the following procedures:

9.3.1 Pre-screening (day 1)

- Eligibility check (CAP clinically diagnosed and age of 3-17 years).
- Information on and obtaining of the **written screening consent**.

Each study site will determine the most efficient procedures to identify potentially eligible patients.

9.3.2 Screening (day 1)

Participation in screening phase:

- Capillary blood for *Mp* IgM LFA (or directly venous blood if IV line or venous blood sample required for clinical reasons).
- NPS for *Mp* PCR (if a NPS is performed for clinical reasons, remaining sample will be stored locally, and transferred later in batches to the MYTHIC Biobank at University Children's Hospital Zurich, so that no more than one swab will be performed on patients on day 1).

9.3.3 Enrollment (day 1)

The *Mp* IgM LFA result will be available within 10min, and in case of a positive result, the following procedures will be performed:

Participation in intervention phase:

- Careful check for inclusion and exclusion criteria.
- Information on and obtaining of the **written informed consent**.
- Venous blood sampling for *Mp* IgM ASC ELISpot assay. Venous blood sampling is often routinely available because an IV line and/or venous blood sampling is performed for clinical reasons in many CAP patients presenting to the hospital. However, the venous blood sample is not required for study inclusion (to avoid exclusion because of refusal to draw blood for the study).

Clinical assessment:

- Medical history (e.g., duration of cough and/or fever before presentation to the ED).

Laboratory and radiological assessment:

- Capillary blood for biomarkers (could be taken together with the blood sample for the *Mp* IgM LFA).
- Venous blood sampling for *Mp* ELISA (if venous blood is available for the *Mp* IgM ASC ELISpot assay).
- CXR (no inclusion criteria but desirable to confirm the clinical diagnosis and often routinely performed in cases with CAP presenting to the hospital).

9.3.4 Randomization (day 1)

- IMP dispensing.

Clinical assessment:

- Physical examination.
- VS (T, RR, HR, SpO₂) just prior to and/or the last time before randomization (or prior to the administration of antipyretic medication at the ED).
- Symptom review incl. AEs.
- Concomitant care review.

9.3.5 Treatment phase (day 1-5)

- IMP administration.

Clinical assessment:

Every day until 3 consecutive normal measurements of all VS within 24h are documented (or at least until discharge) the following procedures will be performed:

- VS (T, RR, HR, SpO₂) measured every 8h for hospitalized patients or 3x/24h for ambulatory patients, *for co-primary outcome 1.1* (section 5.1).
- Symptom review, including AE's, *for secondary outcomes 2.1, 2.2, and 2.5* (section 5.2).

- Concomitant care review,
for *co-primary outcome 1.2* (section 5.1) and *secondary outcome 2.1* (section 5.2).

9.3.5.1 In-hospital study visit day 3 (time window day 3-5)

The following will be performed at the day 3 in-hospital study visit (day 3-5 in trial):

Clinical assessment:

- Physical examination.
- VS (T, RR, HR, SpO₂).
- Symptom review incl. AEs.
- Concomitant care review.
- QoL assessment,
for *secondary outcomes 2.3 and 2.4* (section 5.2).

Laboratory and radiological assessment:

- Capillary blood for biomarkers.
- NPS for *Mp* PCR.

9.3.6 FUP (day 6-28)

9.3.6.1 Daily clinical assessment until normalization of VS

Every day until 3 consecutive normal measurements of all VS within 24h are documented (or at least until discharge) the following procedures will be performed:

- VS (T, RR, HR, SpO₂) measured every 8h for hospitalized patients or 3x/24h for ambulatory patients,
for *co-primary outcome 1.1* (section 5.1).
- Symptom review, including AE's,
for *secondary outcomes 2.1, 2.2, and 2.5* (section 5.2).
- Concomitant care review,
for *co-primary outcome 1.2* (section 5.1) and *secondary outcome 2.1* (section 5.2).

9.3.6.2 Phone call study visits

The following will be recorded on day 7 (time window ± 1 day, day 6-8), day 14 (time window ± 2 day, day 12-16), and day 21 (time window ± 3 day, day 18-24):

Clinical assessment:

- VS (T, RR, HR, SpO₂), if not yet 3 consecutive normal measurements of all VS within 24h are documented.
- Symptom review incl. AEs.
- Concomitant care review.
- QoL assessment.

9.3.7 Close-out visit (day 28)

The following will be performed in the hospital at the close-out visit on day 28 (time window ± 4 day, day 24-32):

Trial participation:

- IMP bottle return (to measure the final height of bottle-content).
- Study diary/worksheet return (if not documented via patient self-documentation with secuTrial®).
- Return of trial box return with ear thermometer and mobile pulse oximeter.

Clinical assessment:

- Physical examination.
- VS (T, RR, HR, SpO₂).
- Symptom review incl. AEs.
- Concomitant care review.
- QoL assessment.

Laboratory and radiological assessment:

- Capillary blood for biomarkers.
- NPS for *Mp* PCR.

10. SAFETY

The principles of GCP require that both investigator and sponsor follow specific procedures when notifying and reporting adverse events or reactions in clinical trials. These procedures are described in this section of the protocol.

10.1 Drug studies

During the entire duration of the study, all AEs (section 5.2, Table 2, and section 9.2.4) and all serious adverse events (SAEs) are collected and documented in the secuTrial®. Study duration encompasses the time from when written informed consent is obtained until the last protocol-specific procedure has been completed.

10.1.1 Definition and assessment of (serious) adverse events and other safety related events

The definitions of ICH E6 [2] based on the principles of GCP apply to this trial protocol (Table 8).

Table 8. Definitions for safety reporting in this study based on ICE E6 definitions [2].

Term	Definition
Adverse Event (AE)	Any untoward medical occurrence in a patient or clinical trial subject to whom a medicinal product has been administered including occurrences which do not necessarily have a causal relationship with the study procedure. An AE can therefore be any unfavorable and unintended sign (including an abnormal laboratory finding), symptom, or disease temporally associated with the use of a medicinal (investigational) product, whether or not related to the medicinal (investigational) product.
Adverse Reaction (AR)	Any untoward and unintended response to an investigational medicinal product related to any dose administered.
Unexpected Adverse Reaction (UAR)	An "unexpected" adverse drug reaction is an AR, the nature or severity of which is not consistent with the applicable product information (e.g., Investigator's Brochure for drugs that are not yet approved and Product Information for approved drugs, respectively).
Serious Adverse Event (SAE) or Serious Adverse Reaction (SAR)	Respectively any AE or AR that: 
• Results in death• Is life-threatening*• Requires hospitalization or prolongation of existing hospitalization**• Results in persistent or significant disability or incapacity• Is another important medical condition*** In addition, important medical events that may not be immediately life-threatening or result in death, or require hospitalization, but may jeopardize the patient or may require intervention to prevent one of the other outcomes listed above should also usually be considered serious. Medical judgement should be exercised in deciding whether an AE or AR is serious.
Suspected Unexpected SAR (SUSARs)	The Sponsor-Investigator evaluates any SAE that has been reported regarding seriousness, causality, and expectedness. If the event is related to the investigational product and is both serious and unexpected, it is classified as a SUSAR.

* The term life-threatening in the definition of a serious event refers to an event in which the patient is at risk of death at the time of the event; it does not refer to an event that hypothetically might cause death if it would be more severe, for example, a silent myocardial infarction.

** Hospitalization is defined as an inpatient admission, regardless of length of stay, even if the hospitalization is a precautionary measure for continued observation. SAE exemptions are hospitalizations for a pre-existing condition that has not worsened or for an elective procedure. These do not constitute an SAE.

*** An example of such an event potentially encountered in MYTHIC is transfer from general ward to ICU.

In MYTHIC, solicited AEs (section 5.2) must be assessed, and if positive, graded at each study visit according to Table 2 (section 5.2) and documented in secuTrial®. SAEs should be followed until resolution or stabilization. Participants with ongoing SAEs at study termination will be further followed up until recovery or until stabilization of the disease after 30 days of termination.

Assessment of causality:

Both investigator and sponsor make a causality assessment of the event to the study drug, based on the criteria listed in Table 9 and in accordance with ICH E2A guidelines [82].

Assessment of severity:

The severity of all symptoms and signs observed during SAEs in MYTHIC should be graded using the solicited AEs grading (section 5.2, Table 2).

Table 9. Criteria for causality assessment of the SAE in accordance with ICE E2A guidelines [82].

Relationship	Description	SAE type
Unrelated	There is no evidence of any causal relationship.	Unrelated SAE
Unlikely	There is little evidence to suggest that there is a causal relationship (for example, the event did not occur within a reasonable time after administration of the trial medication). There is another reasonable explanation for the event (for example, the patient's clinical condition, other concomitant treatment).	Unrelated SAE
Possible	There is some evidence to suggest a causal relationship (for example, because the event occurs within a reasonable time after administration of the trial medication). However, the influence of other factors may have contributed to the event (for example, the patient's clinical condition, other concomitant treatments).	SAR
Probable	There is evidence to suggest a causal relationship and the influence of other factors is unlikely.	SAR
Definitely	There is clear evidence to suggest a causal relationship and other possible contributing factors can be ruled out.	SAR

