4.3 Secondary objectives

The secondary objectives include the evaluation of:

2.1: Overall clinical outcome based on benefits and harms (desirability of outcome ranking [DOOR] and response adjusted for duration of antibiotic risk [RADAR] approach).

2.2: Time (days) to normalization of CAP-related symptoms (i.e., cough, shortness of breath, wheeze, chest pain, sore throat, nasal congestion or runny nose, headache, muscle aches or pains, nausea or vomiting, diarrhea, reduced general condition, decreased appetite, not sleeping well, reduced activity).

2.3: Quality of life (QoL) assessment of the patient's family.

2.4: Time (days) to return to the patient's daily routine, defined as return to childcare/school/work of patients and their families.

2.5: Development of *Mp*-associated extrapulmonary manifestations.

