5.2 Secondary outcomes

A number of secondary and additional outcomes have been defined as relevant endpoints for antibiotic trials in childhood CAP by the IDSA [62].

2.1: Overall clinical outcome based on benefits and harms (DOOR/RADAR approach)

According to documentation of clinical response (normalization of all VS) and solicited AEs 1x/24h at the end of treatment (day 5) and each FUP visit.

Specific measurement: Documentation of clinical response (normalization of all VS, section 5.1) and solicited AEs (Table 2) 1x/24h at the end of treatment (day 5) and at each FUP visit.

Analysis metric: Desirability of outcome ranking (DOOR) [65].

Method of aggregation: Probability of better DOOR.

Time point: Day 3 (in-hospital visit), day 5 (end of treatment), day 7, 14, 21 (phone calls), and day 28 (close-out visit).

Rationale: The novel *response adjusted for duration of antibiotic risk* (RADAR) methodology utilizes a superiority design [65]. In RADAR, all trial participants are assigned a DOOR. The DOOR is constructed using a 2-step process: (1) categorization of all patients into an overall clinical outcome (Table 3), and (2) ranking participants in the trial using 2 rules: (2a) when ranking the outcomes of 2 patients with different overall clinical outcomes, the patient with a better overall clinical outcome receives a higher rank; and (2b) when ranking the outcomes of 2 patients with the same overall clinical outcome, the patient treated with placebo receives a higher rank. These DOOR ranks are then compared between the treatment arms with regard to the probability of a better DOOR for a randomly selected patient with placebo vs. azithromycin (i.e., Wilcoxon-Mann-Whitney statistic [66]). The DOOR/RADAR approach is helpful for RCTs to define the optimal therapeutic strategy, since considering exclusively the primary endpoint may not allow researchers to accurately balance a proven benefit with other potential harms (i.e., impaired effectiveness or side effects/AEs).

Table 2: Solicited adverse events (AEs) grading [66, 67].

Symptom	Mild (grade 1)	Moderate (grade 2)	Severe (grade 3)
Diarrhea	Looser than normal stools occurring 3-6 times/day	Looser than normal stools occurring >6 times/day	Bloody diarrhea, or diarrhea that requires medical intervention, laboratory testing, or hospitalization
Vomiting	1 episode/day	2-3 episodes/day	≥ 4 episodes/day

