Abdominal pain	Mild or intermittent and does not interfere with daily activity	Moderate or persistent and interferes with daily activity but did not need a medical visit or absenteeism from daily routine	Prevents daily activity and resulted in medical visit or absenteeism
Allergic reaction (rash and/or pruritus)	Localized rash or pruritus without rash	Diffuse rash (maculopapular or urticarial)	Generalized rash consistent with Stevens-Johnson syndrome, erythema multiforme, or toxic epidermal necrolysis; anaphylaxis; or angioedema
Oral/pharyngeal thrush or nappy rash (Candidiasis)	Mild mucocutaneous candidiasis or diaper dermatitis, with no treatment or topical treatment only	Moderate mucocutaneous candidiasis requiring oral antimicrobial treatment	Severe mucocutaneous candidiasis; requires medical intervention, intravenous treatment, or hospitalization

Table 3: Overall clinical outcome.

Outcome	Adequate clinical response*	Solicited AEs**
1	Yes: normalization of all VS	No
2	Yes: normalization of all VS	Mild (grade 1)
3	Yes: normalization of all VS	Moderate (grade 2)
4	Yes: normalization of all VS	Severe (grade 3)
5	No: no normalization of all VS without additional ED or clinic visit or hospitalization	Any grade
6	No: no normalization of all VS with additional ED or clinic visit but without hospitalization	Any grade
7	No: no normalization of all VS with hospitalization (admission, re-admission, or ongoing hospitalization)	Any grade
8	Death (any cause)	

* Adequate clinical response defined by the co-primary outcome normalization of all VS (section 5.1).

** Solicited AEs are defined in Table 3.

2.2: Time (days) to normalization of CAP-related symptoms (i.e., cough, shortness of breath, wheeze, chest pain, sore throat, nasal congestion or runny nose, headache, muscle aches or pains, nausea or vomiting, diarrhea, reduced general condition, decreased appetite, not sleeping well, reduced activity).

Specific measurement: Documentation of symptoms 1x/24h according to a validated measure for childhood respiratory infections [68, 69] by parent and the child until normalization.

Analysis metric: Time to event (days).

Method of aggregation: Hazard/median time to event.

Time point: Time point of resolution of all CAP-related symptoms.

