11.4.5 Safety analysis

Safety will be assessed via:

- Analysis of the safety outcomes as detailed in section 5.4: proportion of children with CAP-related change in patient care status (1.2), overall clinical outcome based on benefits and harms (DOOR/RADAR approach, 2.1), development of *Mp*-associated extrapulmonary manifestations (2.4), unscheduled medical visits, (re-)treatment with antibiotics, and side effects/AEs/SAEs of IMP.
- Rigorous and detailed examination of side effects/AEs/SAEs of IMP. Frequencies and types of AEs will be reported per study arm, together with the proportion of patients experiencing AEs.
- Interim analysis for safety after $1/3$ and $2/3$ of the patients have completed the 28-day FUP (section 11.4.4).

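### Vomiting and diarrhea that persist from the pneumonia count as solicited adverse events in both arms, which attenuates the per-arm AE comparison

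*Protocol*

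**What the plan says.** **Capture window.** Section 10.1 states that "all AEs (section 5.2, Table 2, and section 9.2.4) and all serious adverse events (SAEs) are collected" over the whole study, and that "Study duration encompasses the time from when written informed consent is obtained until the last protocol-specific procedure has been completed". Consent comes before randomization and the first dose. Table 8 in section 10.1.1, however, defines an AE for a subject who has received a medicinal product, and section 10.1.2 starts SAE reporting at randomization.

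**Grading rule.** Section 10.1.1: "solicited AEs (section 5.2) must be assessed, and if positive, graded at each study visit according to Table 2". Table 2 grades diarrhea and vomiting mainly by daily frequency; grade 1 diarrhea is "Looser than normal stools occurring 3-6 times/day". Neither the rule nor the table mentions onset after the first dose or change from entry.

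**Disease symptoms.** The synopsis, section 4.3 and section 5.2 (outcome 2.2) list CAP-related symptoms that include "nausea or vomiting, diarrhea, reduced general condition, decreased appetite". The list for the same outcome in section 9.2.2 contains neither vomiting nor diarrhea.

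**Entry assessment.** Section 9.3.4 schedules "Symptom review incl. AEs" at randomization. No section uses it as a baseline for later AE grading.

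**Use.** Section 11.4.5 reports AE frequencies and types per arm, "together with the proportion of patients experiencing AEs". By section 9.2.4.1 the same graded events feed DOOR, where they separate categories 1 to 4 of Table 3.

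**The concern.** By the protocol's own lists, the same loose stools can be a symptom of the pneumonia under outcome 2.2 and a solicited AE under section 10.1.1. A child who enters with diarrhea and still has it on day 3 becomes an AE case whatever the allocated treatment. Such cases raise both arms alike and bring them closer together.

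The affected items matter. Sections 3.3 and 3.6 name gastrointestinal effects as the main known harm of azithromycin, and section 11.2 defends the 1.5-day margin partly by weighing it against side effects. That argument needs a harm comparison that is not blurred by symptoms the children brought with them.

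**Working it through.** **1. Can illness symptoms enter the AE count?** The capture window and Table 8 disagree about events before the first dose. Under Table 8, an episode that starts and ends before dosing is not an AE. A symptom still present at a visit after dosing is positive and is graded under either reading. Table 9 gives causality criteria for SAEs only, so it removes no non-serious solicited event. Section 10.1.1 does exempt hospitalization for an unworsened pre-existing condition from SAE status, but no similar rule covers solicited AEs. The route is therefore open for symptoms that persist past the first dose.

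**2. Which items overlap?** Vomiting and diarrhea, two of the five in Table 2. Abdominal pain, allergic reaction and candidiasis are in no CAP symptom list.

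**3. Size in an ever/never proportion.**

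Inputs:
- d, the excess on azithromycin: section 3.6 gives 5.8% for diarrhea and 1.9% for vomiting as rates attributed to the drug. Here they are taken as the excess over placebo, which is an assumption.
- p, new onset on placebo: not in the protocol; 2% assumed, range 0 to 5%.
- b, the share whose entry symptom is counted: not in the protocol; 0 to 30% assumed.
- n: 376 enrolled, 1:1, so 188 per arm. The 376 itself checks to within one patient. With z-values 2.241 and 0.842, (2.241 + 0.842)² × 2 × 0.05 × 0.95 / 0.075² = 160.5, so 161 per arm and 322 in total; 322 / 0.855 = 376.6.

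Formulas:
- placebo = b + (1−b)p
- azithromycin = b + (1−b)(p+d)
- risk difference = (1−b)d
- risk ratio = 1 + (1−b)d / [b + (1−b)p]
- 95% CI half-width = 1.96 × √[(sum of the two p(1−p) terms) / 188]

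Diarrhea, d = 5.8%, p = 2%:

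| b | Placebo | Azithromycin | Difference (points) | Ratio | CI half-width (points) |
|---|---|---|---|---|---|
| 0 | 2.0% | 7.8% | 5.8 | 3.90 | 4.3 |
| 5% | 6.9% | 12.4% | 5.5 | 1.80 | 5.9 |
| 10% | 11.8% | 17.0% | 5.2 | 1.44 | 7.1 |
| 20% | 21.6% | 26.2% | 4.6 | 1.21 | 8.6 |
| 30% | 31.4% | 35.5% | 4.1 | 1.13 | 9.5 |

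The difference does not depend on p. At b = 10% the ratio runs from 1.52 (p = 0) to 1.36 (p = 5%). For vomiting, with d = 1.9% and p = 2%, the ratio is 1.95 at b = 0, 1.14 at 10% and 1.07 at 20%.

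The direction holds for every b above 0. The absolute difference moves modestly; the ratio and the precision move more.

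**4. DOOR.** It is scored on days 3, 5, 7, 14, 21 and 28, not at entry. In Table 3 solicited AEs change the category only when all vital signs have normalized; categories 5 to 7 take any grade. The relevant share is therefore persistence to a scored day in a recovered child, which is smaller than prevalence at entry.

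**The case against.** **It is SAP material.** Restricting safety tables to treatment-emergent events is usually a SAP matter, section 11.4 defers detail to a SAP, and AE reporting in the protocol is descriptive. This stands for the tabulation. It does not stand for the data. A count of worsened events needs Table 2 grades from before the first dose. Section 9.3.4 does not say that grades are recorded then, and whether the day 1 review counts as a study visit under section 10.1.1 is left open. If the grades are not collected, a later SAP cannot recover them.

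**Stronger readings that the protocol does not support.**
- A reader might infer that all illness before the first dose is counted as an AE. Table 8 points the other way; only persisting symptoms are clearly caught.
- A reader might infer that a child with an entry symptom can add nothing to the contrast. That is true only of an ever/never proportion. Table 2 has three grades, and a rise in grade shows in graded data and in DOOR.
- A reader might extend the overlap to abdominal pain, which is on no CAP symptom list.
- A reader might turn the widening intervals into a loss of power. The protocol plans no test of AE proportions, and b is assumed.

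**The remedy is not neutral for DOOR.** Any-cause symptom burden is a legitimate component of a benefit-harm ranking. Removing same-grade persistent symptoms would also remove illness vomiting that lasts longer without the antibiotic, which could favor placebo. This stands, and it is a reason to leave Table 3 alone.

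**Conclusion.** The point holds in limited form. The protocol sets a grading rule without a baseline and a capture window that disagrees with its own AE definition, and two solicited items are also disease symptoms. Vomiting or diarrhea that persists past the first dose is counted as an AE in both arms.

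Under blinded 1:1 allocation this contamination is equal in expectation, so it attenuates the contrast and does not reverse it. The risk difference shrinks by 1−b: from 5.8 to 5.2 points of diarrhea at an assumed b of 10%, with the ratio falling from 3.90 to 1.44 if new onset on placebo is 2%. The formula is certain for an ever/never count. The size is not, because b and p are assumed and the 5.8% is treated as an excess over placebo.

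No co-primary analysis, margin, significance level or sample size is affected, and the effect on DOOR is confined to symptoms lasting to day 3 or later after vital signs have normalized. It is worth correcting because it is cheap and because the entry grades are hard to reconstruct afterwards.

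**What to change.** 1. Reconcile the capture window in section 10.1 with the AE definition in Table 8, and the symptom lists in the synopsis and sections 4.3 and 5.2 with the list in 9.2.2.
2. State in sections 9.3.4 and 10.1.1 that the Table 2 items are graded at the existing day 1 symptom review, before the first IMP dose.
3. In section 11.4.5, make the main proportion the patients with a solicited AE that is new, or of a higher grade than at that review, after the first dose. Show any-cause presence per visit and arm alongside.
4. Leave DOOR Table 3 as any-cause, and add a sensitivity analysis that counts only new or worsened solicited AEs.

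**Cost.** A few sentences, grading at a review that already takes place, and one extra DOOR run. No visit or sample is added. The drawback is that same-grade prolongation of an entry symptom, whether from drug or illness, appears only in the any-cause table, so the two tables must be read together.
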